#### Serious Adverse Event

Adverse events are classified as serious or non-serious.

A **serious adverse event** is any AE that is:

- fatal

247           • life-threatening  
248           • requires or prolongs hospital stay  
249           • results in persistent or significant disability or incapacity  
250           • a congenital anomaly or birth defect  
251           • an important medical event

252  
253           Important medical events are those that may not be immediately life threatening, but are  
254           clearly of major clinical significance. They may jeopardize the subject, and may require  
255           intervention to prevent one of the other serious outcomes noted above. For example, drug  
256           overdose or abuse, a seizure that did not result in in-patient hospitalization or intensive  
257           treatment of bronchospasm in an emergency department would typically be considered  
258           serious.

259  
260           All adverse events that do not meet any of the criteria for serious should be regarded as  
261           ***non-serious adverse events.***

262           Adverse Event Reporting Period

263           The study period during which adverse events must be reported is normally defined as the  
264           period from the initiation of any study procedures to the end of the study treatment follow-  
265           up. For this study, the study treatment follow-up starts at randomization and ends at 90  
266           days after the surgery.

267           Preexisting Condition

268           A preexisting condition is one that is present at the start of the study. A preexisting  
269           condition should be recorded as an adverse event if the frequency, intensity, or the  
270           character of the condition worsens during the study period.

271           General Physical Examination Findings

272           At screening, any clinically significant abnormality should be recorded as a preexisting  
273           condition. At the end of the study, any new clinically significant findings/abnormalities  
274           that meet the definition of an adverse event must also be recorded and documented as an  
275           adverse event.

276           Post-study Adverse Event

277           All unresolved adverse events should be followed by the investigator until the events are  
278           resolved, the subject is lost to follow-up, or the adverse event is otherwise explained. At  
279           the last scheduled visit, the investigator should instruct each subject to report any  
280           subsequent event(s) that the subject, or the subject's personal physician, believes might  
281           reasonably be related to participation in this study. The investigator should notify the study  
282           sponsor of any death or adverse event occurring at any time after a subject has discontinued  
283           or terminated study participation that may reasonably be related to this study. The sponsor  
284           should also be notified if the investigator should become aware of the development of  
285           cancer or of a congenital anomaly in a subsequently conceived offspring of a subject that  
286           has participated in this study.

287           Abnormal Laboratory Values

288           A clinical laboratory abnormality should be documented as an adverse event if any one of  
289           the following conditions is met:

290           • The laboratory abnormality is not otherwise refuted by a repeat test to confirm the  
291           abnormality  
292           • The abnormality suggests a disease and/or organ toxicity

293           • The abnormality is of a degree that requires active management; e.g. change of  
 294           dose, discontinuation of the drug, more frequent follow-up assessments, further  
 295           diagnostic investigation, etc.

296           Hospitalization, Prolonged Hospitalization or Surgery

297           Any adverse event that results in hospitalization or prolonged hospitalization should be  
 298           documented and reported as a serious adverse event unless specifically instructed otherwise  
 299           in this protocol. Any condition responsible for surgery should be documented as an  
 300           adverse event if the condition meets the criteria for an adverse event.

301           Neither the condition, hospitalization, prolonged hospitalization, nor surgery are reported  
 302           as an adverse event in the following circumstances:

- 304           • Hospitalization or prolonged hospitalization for diagnostic or elective surgical  
 305           procedures for a preexisting condition. Surgery should **not** be reported as an  
 306           outcome of an adverse event if the purpose of the surgery was elective or  
 307           diagnostic and the outcome was uneventful.
- 308           • Hospitalization or prolonged hospitalization required to allow efficacy  
 309           measurement for the study.
- 310           • Hospitalization or prolonged hospitalization for therapy of the target disease of the  
 311           study, unless it is a worsening or increase in frequency of hospital admissions as  
 312           judged by the clinical investigator.

313           8.2 Recording of Adverse Events

314           At each contact with the subject, the investigator must seek information on adverse events by  
 315           specific questioning and, as appropriate, by examination. Information on all adverse events  
 316           should be recorded immediately in the source document, and also in the appropriate adverse event  
 317           module of the case report form (CRF). All clearly related signs, symptoms, and abnormal  
 318           diagnostic procedures results should be recorded in the source document, though should be  
 319           grouped under one diagnosis.

320           All adverse events occurring during the study period must be recorded according to the following:

Adverse event	Start date	SAE* 1. Yes (also complete SAE form) 2. No	Causality 1. Unrelated 2. Possibly Related	Severity 1. Mild 2. Moderate 3. Severe	Expectedness 1. Expected 2. Unexpected	DATE of assessment and INITIALS of delegated clinician	Outcome 1. Resolved 2. Ongoing	Date Resolved	AE Recorded by (initials)

324  
325  
326 The clinical course of each event should be followed until resolution, stabilization, or until it has  
327 been determined that the study treatment or participation is not the cause. Serious adverse events  
328 that are still ongoing at the end of the study period must be followed up to determine the final  
329 outcome. Any serious adverse event that occurs after the study period and is considered to be  
330 possibly related to the study treatment or study participation should be recorded and reported  
331 immediately.

332 **8.4 Stopping Rules**

333 We will do an interim analysis after reaching 50 patients, and if there is a significant  
334 difference (> 20%) in post operative mortality or morbidity in one group versus the other,  
335 then the study will be discontinued.

336 **8.5 Data and Safety Monitoring Plan**

337 It is the responsibility of the Principal Investigator to oversee the safety of the study at his/her  
338 site. This safety monitoring will include careful assessment and appropriate reporting of adverse  
339 events as noted above, as well as the compliance and implementation of the KCC data and safety-  
340 monitoring plan. Medical monitoring will include a regular assessment of the number and type of  
341 serious adverse events by both the assigned Medical Monitor and the KCC DSMC.  
342  
343

344 **8.5.1 Medical Monitoring and AE/SAE Reporting**

345 A Medical Monitor is assigned to this study at the Thomas Jefferson University. This is a  
346 physician/pharmacist who is not directly involved in the trial, and is not currently collaborating with  
347 the sponsor/investigator on any other trial. The role of the Medical Monitor is to review all  
348 reportable AEs/SAEs (in real-time) including grading, toxicity assignments, non-reportable AEs  
349 (quarterly), protocol violations/deviations, as well as all other safety data and activity data observed  
350 in the ongoing clinical trial occurring at the participating sites and at Thomas Jefferson University.  
351 The Medical Monitor may recommend reporting of adverse events and relevant safety data, and may  
352 also recommend suspension or termination of the study to the DSMC and TJU IRB.  
353

354 Every KCC investigator initiated protocol includes requirements for reporting of adverse events  
355 based on CTC 4.0. All events are reported to the IRB and Medical Monitor using a password  
356 protected web-site. In addition all unexpected and serious adverse events (SAEs) are reported to  
357 the TJU IRB and to the Food and Drug Administration (FDA) if applicable. The investigator is  
358 required to submit all unexpected and serious adverse events to the TJU IRB and the Medical  
359 Monitor within the timeframes outlined in the below table. All AE/SAEs will be reported to the  
360 DSMC at the quarterly DSMC review meetings; however, if the Medical Monitor determines  
361 corrective action is necessary, an “ad hoc” DSMC meeting will be called. ***Fatal adverse events  
362 related to treatment which are unexpected must be reported within 24 hours to the TJU IRB  
363 and the DSMC. Fatalities not related to the study drug/device must be reported within 5 days***  
364

365 **8.5.2 Data and Safety Monitoring Committee**

366 Data and Safety Monitoring Committee (DSMC) is the Data and Safety Monitoring Board  
367 (DSMB) for the KCC. The DSMC is a multidisciplinary committee charged with overseeing the  
368 monitoring of safety of participants in clinical trials, and the conduct, progress, validity, and  
369 integrity of the data for all clinical trials at the Thomas Jefferson University KCC. The committee  
370 meets quarterly to review the progress and safety of all active research protocols that are not  
371 monitored by another safety and data monitoring committee or board.

372       • The DSMC meets quarterly. Additional DSMC meetings are scheduled based on the  
373       nature and number of trials being monitored over a specified time period. The DSMC  
374       meets (by conference call) within 24 hours following the notification of an  
375       unexpected adverse event felt to be related to the study drug.  
376       • Prior to each DSMC meeting, each board member, is provided a printout of all  
377       reported AEs and SAEs occurring during the reporting period for this clinical trial.  
378       The principal investigator provides a detailed and comprehensive narrative  
379       assessment of current adverse events to date, indicating their possible significance and  
380       whether these toxicities have affected the conduct of the trial. DSMC members are  
381       provided with the principal investigator's assessment, a written report summarizing  
382       adverse events, safety data, and activity data observed during the specified time  
383       period described in each protocol, as well as  
384

385       recommendations from the Medical Monitor. A review of outcome results (response,  
386       toxicity and adverse events) and factors external to the study (such as scientific or  
387       therapeutic developments) is discussed, and the Committee votes on the status of each  
388       study.

389       • A summary of the board's action is sent to each investigator, the CCRRC and TJU  
390       IRBs. The DSMC actions may include recommendations/requirements that will lead  
391       to improved patient safety and/or efficacy, significant benefits or risks that have  
392       developed, or other changes determined to be necessary. The DSMC may also take  
393       note of slow accrual or lack of scientific progress, and refer such issues to the  
394       CCRRC. The DSMC provides the investigator with the rationale for any decision  
395       made.

396       The Thomas Jefferson University Data and Safety Monitoring Committee reviews all  
397       AE/SAE's on open protocols. Therefore, once AE/SAE reports from participating  
398       site are received by the Thomas Jefferson University Coordinating Site, a copy will be  
399       submitted to the TJU IRB/Medical Monitor/DSMB. Medical Monitor and DSMB  
400       review and monitoring of participating site AEs/SAEs will follow the TJU DSMP.  
401

402

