170 The stent will placed by ERCP and won't be removed before surgery unless indicated. Follow up  
171 phone calls to ascertain secondary endpoints will be made at 30 and 90 days.

172 5.7 Prior and Concomitant Therapy  
173 Subject in the study are to continue any medications that they are on. Those who are randomized  
174 to the intervention group may be asked to hold antiplatelet/anticoagulation agents prior to the  
175 ERCP in coordination with their prescribing doctor.

176 5.8 Blinding of Study Drug  
177 Unblinded study

178 **6.0 STUDY PROCEDURES**

179

180 **6.1 Study Visit Schedule**

181 **Screening:**  
182 Patients will be screened in clinic or if admitted as inpatients. Patient must satisfy the inclusion  
183 criteria listed above. Patient must carry a diagnosis of per-ampullary cancer. Basic labs will be  
184 withdrawn including CBC, CMP and INR.

185

186 **Randomization**  
187 **Peri-operative:** The patient will be admitted and labs will obtained including CBC, CMP and  
188 INR prior to surgery.

189

190 **Post-operative:**  
191 Visit 1: This will be scheduled 3-4 weeks after hospital discharge. Labs and imaging may be  
192 ordered by the surgeon if needed.

193 Follow-up  
194 Patients will be followed up to 90 days after the surgery. A phone call will be placed to the  
195 patient by research staff to ascertain secondary endpoints. Jefferson EMR will be accessed  
196 to ascertain primary endpoint data.

197

198 **7.0 STATISTICAL PLAN**

199 7.1 Sample Size Determination  
200 Based on previous data, we assumed an overall grade III or higher complication rate of  
201 50% in the control group. Although we are unsure of the expected rate in the pre-operative  
202 biliary stenting group, a 30% or greater reduction in the grade III or higher complication

would be meaningful. The sample size will be 100 subjects (50 per arm). We calculated power under various alternatives for the biliary stenting group complication rate using a two-group large-sample normal approximation test of proportions, with a one-sided significance level of 0.05, to test the null hypothesis that the grade III or higher complication rate in surgery with biliary stenting is greater than or equal to the control rate (50%). We have 84% power to detect a reduction if the true rate with biliary stenting is 25%, 66% power if the true rate is 30%, and 44% power if the true rate is 35%.

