## 7.2 Statistical Methods

Baseline characteristics will be summarized by randomization arm using means, standard deviations, and ranges for continuous variables and counts and frequencies for categorical variables.

Rates of grade III or higher complication rates will be estimated separately at 30 and 90 days. The risk difference will be calculated (stent minus control) with a one-sided 95% confidence interval. If the upper bound of the confidence interval is less than 0 at both times, surgery with biliary stenting will be considered effective at reducing the rate of grade III or higher complications.

Group comparisons with respect to continuous outcomes will be performed using two-sample t-tests or Wilcoxon rank sum tests. Comparisons for categorical outcomes will be performed using chi-square tests or Fisher's exact test. Comparisons for count outcomes will use Poisson regression. Kaplan-Meier analysis will be used to estimate the distribution of time-to-event outcomes. Groups will be compared using the log rank test.

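### The stop at 50 patients in section 8.4 is undefined and ignored by 7.1 and 7.2, so the stated 5% error and 84/66/44% power do not both hold under most readings of it

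*Combined protocol and SAP*

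**What the plan says.** Section 8.4 (Stopping Rules) reads: "We will do an interim analysis after reaching 50 patients, and if there is a significant" "difference (> 20%) in post operative mortality or morbidity in one group versus the other", "then the study will be discontinued". The stop is mandatory and applies whichever arm does worse.

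Section 7.1 sets the test "with a one-sided significance level of 0.05", with 50 per arm and a 50% control rate. It gives power of 84%, 66% and 44% for stent rates of 25%, 30% and 35%. Section 7.2 declares stenting effective "If the upper bound of the confidence interval is less than 0 at both times" (30 and 90 days), using a one-sided 95% interval for the risk difference. For categorical outcomes generally it adds: "Comparisons for categorical outcomes will be performed using chi-square tests", or Fisher's exact test. Neither section mentions the look.

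Section 5.8 states "Unblinded study". Sections 8.5.1 and 8.5.2 describe a Medical Monitor and a DSMC that votes on the status of each study. They give no boundary and are not assigned the 8.4 analysis.

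**The concern.** The look can decide the trial, yet 8.4 does not say:

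- which morbidity counts (7.1 and 7.2 use grade III or higher; 3.3 lists total complications);
- whether 30 or 90 days applies;
- whether 20% is absolute or relative to control;
- whether significance is a test on top of the 20%, and if so which one;
- whether the 50 patients are randomized or evaluable;
- what may be concluded about efficacy after a stop.

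The last gap matters most. If stenting works as well as 7.1 hopes, an early stop in its favour is a likely outcome, and 7.2 has no rule for it. Different answers give different error rates and different power. Because the study is unblinded, the answer could be settled after the arm results are known. Trials that stop in favour of stenting will also overstate the benefit.

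**Working it through.** **Inputs.** From 7.1: control rate 50%; stent rates 25/30/35%; 50 per arm; one-sided 0.05 (z = 1.645). From 8.4: a look at 50 patients. From 7.2: success if the upper bound is below 0. My assumptions are 25 evaluable per arm at the look, grade III or higher complications, one time point unless stated, a Wald bound (7.2 names no interval method), no dropout, and an absolute gap over 20 points. More than 20% of 25 is more than 5, so the gap is 6 or more patients.

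**1. Reproduce the stated power.** Power = Φ{[δ − z√(2p̄(1−p̄)/n)] / √([p_c(1−p_c) + p_t(1−p_t)]/n)}. At 25%, δ = 0.25 and p̄ = 0.375. The null SE is √(2×0.375×0.625/50) = 0.0968, and the alternative SE is √((0.25+0.1875)/50) = 0.0935. So (0.25 − 1.645×0.0968)/0.0935 = 0.970, and Φ(0.970) = 83.4%. At 30% and 35% the results are 65.7% and 44.9%. The unpooled version gives 84.8/67.0/45.6%. The stated 84/66/44% agrees with both to within two points, so it is the power of a single analysis with no look.

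**2. Add the look.** Exact binomial enumeration at 25 and then 50 per arm. With no look, error is 4.6% at 50%/50% and power is 84.7/67.1/45.2%.

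| | Gap > 20 points | Gap and Fisher p<0.05 |
|---|---|---|
| Stops early, 50% vs 50% | 11.9% | 3.3% |
| Stops early, stent 25/30/35% | 59/45/31% | 36/23/14% |
| Error if a stent-favouring stop is success | 5.95% + 2.49% = 8.4% | 1.64% + 3.70% = 5.3% |
| Power, same reading | 87/71/51% | 85/68/47% |
| Power if a stop supports no claim | 27/27/20% | 49/45/33% |

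The two terms in the error row are stops favouring stenting and wins at the final analysis. Requiring a pooled z-test p<0.05 instead of Fisher gives error 6.4%, and power 38/36/27% when a stop supports no claim. At a 40% rate in both arms the errors are 8.7% (gap) and 6.0% (Fisher), against 5.3% with no look.

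**3. One data set, two answers.** Take 9 events of 25 with stenting and 15 of 25 without. The difference is −0.24, and the Wald upper bound is −0.24 + 1.645×√(0.36×0.64/25 + 0.60×0.40/25) = −0.014, below 0. Fisher's p is 0.16. The trial stops if the gap alone decides and continues if Fisher is also required.

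**4. Re-apply the 7.2 both-times rule at the stop.** This needs 30/90-day rates that the documents do not give. In simulation with 30-day events nested in 90-day events, error is about 4.4% for null rates of 40/50% and 5.5% for 45/50% (no look: 2.5% and 3.0%). It rises as the two rates approach each other: about 6.5% at 47.5/50% and 7.4% at 49/50%. Power at a 25% stent rate is 63–78%, against 70–78% with no look, so most of that shortfall comes from the both-times rule and 0–7 points from the look.

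**5. Exaggeration.** Under the gap rule, the mean observed difference at stent-favouring stops is −34/−32/−31 points, against true −25/−20/−15.

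**6. A boundary for comparison.** Lan-DeMets O'Brien-Fleming spending at half the information is 2[1 − Φ(1.96/√0.5)] = 0.0056, so z = 2.538 at the look and 1.662 at the end (p<0.048). Exact error is 4.8% (5.3% at a 40% rate), and power is 84.3/66.3/44.7%.

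**The case against.** The rule sits in the safety section, speaks only of discontinuing, and never calls a stop a success. The only efficacy criterion is in 7.2. The 8.4% error therefore rests on a success rule that the documents do not contain. That stands, and 8.4% should not be read as the trial's error rate.

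The word significant, read with the tests in 7.2, naturally suggests a test as well as the 20% gap. With Fisher, and a stent-favouring stop counted as success, error is 5.3% and the stated power is met. This also stands. It weakens two stronger inferences a reader might draw. One is that most of the power is lost whenever a stop is not a success: with Fisher, 49/45/33% remains. The other rests on reading 20% as relative with no test, where 46% of null trials would stop; that reading disregards the word significant.

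The defence is incomplete, though. 8.4 does not refer to those tests, and the favourable Fisher result also needs a stop to count as success, which is equally unstated. Reading the rule as pure safety does not rescue it either: it is symmetric, so a stop with no efficacy claim is exactly the case that loses power. The Medical Monitor and DSMC lessen the risk of a choice made after seeing the data, but 8.4 does not give them the analysis.

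**Conclusion.** The point holds as a failure to fix the rule, with material consequences. Under most readings either the error exceeds 5% or the stated power is not delivered. Both hold approximately if Fisher is required and a stent-favouring stop is success. They also hold if only stenting being worse can stop the trial, but the two-directional wording of 8.4 excludes that.

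A reader might infer that the look inflates the error in every case. The documents do not support this: with no claim at a stop, error falls to 2.5% (gap rule), and with the 7.2 rule re-applied it is about 4.4–5.5% for the 30/90-day rates first assumed, and higher if those rates are closer.

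The figures depend on the assumptions listed with the inputs. The single-time-point results are exact under them. The two-time-point results are less secure because the rates are assumed. Sections 7.1, 7.2 and 8.4 should be reconciled before the look is taken.

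**What to change.** In 8.4, state the endpoint for the efficacy comparison (grade III or higher), the time point or points, the absolute scale, the test, and that the count is of evaluable patients. State also what a stop means for the 7.2 conclusion. Then take one route:

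- **Preferred.** Early efficacy may be claimed only by a prespecified group-sequential boundary applied to the 7.2 criterion. The O'Brien-Fleming boundary above is one example: one-sided p<0.0056 at the look, p<0.048 at the end. Carry the adjusted final bound and the power (about 84/66/45% for one time point) into 7.1 and 7.2.
- **Alternative.** Declare that the look cannot stop for benefit. Power is unchanged (84.7/67.1/45.2%) only if the sole statistical stop is for stenting being worse. A guideline that also acts on excess complications with direct surgery brings the power loss back.
- **If a two-directional stop is kept,** restate both power and error. Restating power alone would leave any inflation uncorrected.

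Leave harm and mortality decisions to the existing DSMC.

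The cost is protocol wording and, for the preferred route, 0.4–0.8 points of power at one time point. Its downside is fewer early stops for apparent benefit: 28% instead of 59% at 25% versus 50%.
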